be severe. In a large-scale study of CPT for veterans with military-related PTSD, researchers reported the most significant “attributed” or “possibly attributed” adverse event for any of the study treatment (psychiatric hospitalization), was “attributed” in only 1 out of 461 CPT participants (0.002%) and “possibly attributed” in 6 out of 461 CPT participants (0.01%) [51]. This indicates that severe adverse events, such as psychiatric hospitalization, are rare in the context of this study and unlikely to be attributable to CPT treatment.

One other risk of taking part in this study is that the participant’s study information could become known to someone who is not involved in the study. For instance, someone might find out that the participant has a history of trauma. Breaking confidentiality in this way could happen if any of the data we collected were to be lost or stolen from the laboratory or if any data stored in the electronic database were damaged.

Multiple Sites:

All data for this study will be collected at OCI, FLCI, or TCI. [name] and his staff have an extensive and ongoing program of psychological research with residents at all three sites. Neither the prisons nor the Wisconsin Department of Corrections (DOC) has a legally constituted IRB. However, the DOC has a formal Research Review Committee. Before conducting research with the DOC, it is necessary for investigators to receive both approval by a legally constituted IRB and the DOC Research Review Committee.

Research activities conducted at non-UW sites (OCI, FLCI, TCI) will be monitored by experienced research staff (graduate students, Research Specialists, P.I.) to ensure that the activities are within the guidelines of the protocol. Research team members will be trained to conduct the research activities according to IRB guidelines and will immediately report any complications to the research staff and the P.I. The P.I. will meet weekly with the entire study team to ensure regular communication regarding the study procedures. Any unanticipated problems, adverse events, or protocol deviations will be monitored by the study therapists and will then be reported to [name]. Examples of potential reportable events include participant drop out due to unexpectedly high emotional distress from participating in the group or a participant report of significant increase in suicidal ideation. [name] will relay these events to the UW-Madison HS-IRB. If any protocol changes are necessary in response to an unanticipated problem, [name] will communicate this to the UW-personnel working on the study, and the study therapists will monitor such changes on-site to ensure they are followed.

Because the multiple study sites are not involved in the research study (the studies are simply conducted at these sites), communication between research staff and the study sites is limited to logistics of scheduling (e.g., reserving rooms in the prison). Specific study information (e.g., protocol updates) will not be disseminated to the study sites.

The UW-Madison HS-IRB is the only IRB that will be approving documents and consent forms for this study. Therefore, there is no need to review IRB approved documents from other sites.

Monitoring and Reporting Adverse Events:

A serious adverse event can be classified as life threatening, requires inpatient hospitalization, persistent or significant disability or incapacity, or is an important medical event[51].

Participants will be monitored by a study therapist or study team member during all study visits. Study visits include baselines, follow up interviews, treatment groups, and focus groups. At the start of every session, the study team or therapist will hand out an independent sheet for each participant with the following questions,

1. “Have you had any significant/negative psychological, social, physical, or other negative life events in the last week? ”
2. How did this event make you feel?
3. When did this situation happen?
4. Is the situation ongoing? If not what day/date did it end?
5. What this situation related to this treatment?

Once finished, the therapist will collect the document and check the response. The response to this question will be tracked and monitored each session. If the adverse events needs follow up, the therapist or study team member will have a conversation with the participant.

The study therapist and study team members will be required to notice any clinically significant changes in PTSD symptoms or any worsening symptoms and determine adverse events. The study team or study therapists will perform structured assessments (i.e., PCL-5, PHQ-9) each the beginning of each group. We will add a 15-minute period at the beginning of each group session specifically for check-ins and administration of the PCL-5 and PHQ-9. Scores from the PCL-5 and PHQ-9 will be reviewed during this period, and will be added to a tracking document that has separate columns for each measure at each timepoint assessment (i.e., baseline, group sessions, midpoint, post-treatment). The tracking document will also include columns to indicate whether the PCL-5 score has increased by 10 or more points and whether the participant reported a 1, 2, or 3 on item 9 of the PHQ-9. Additionally, a research staff member will stay in the treatment room to assist the study therapist with administration, review, tracking of the participant scores, and assessment of SI via the C-SSRS-SV as needed.

The study team will conduct the BDI-II at each timepoint assessment (baseline, mid-, post-, 1 month, 3 month follow up) . We will also use a tracking procedure to document BDI-II scores including whether the participant reported a 2 or 3 on item 9. Additionally, a research staff member will administer, review, and track the participant score, and assessment of SI via the C-SSRS-SV as needed.

Each change in the PCL-5 or the PHQ-9/BDI-II that meets the definition of an AE will be reported appropriately and tracked in REDCap.

If the participant exhibits any significant or unexpected psychological symptoms, social issues, physical injuries, or medical injuries during the study the therapist/study team will talk one on one about their symptoms and continuation in the group. They will encourage participants to reach out to psych services during these one-on-one conversations. Some studies have found temporary exacerbations of PTSD symptoms and temporary increases in depression, anxiety, and sleep disturbance symptoms for a subset of participants during PTSD treatment [58, 54]. Importantly

though, for participants who saw an increase in PTSD symptoms, the increase was temporary and they still experienced clinically significant improvement by the end of treatment, indicating the treatment's safety [57]. Similarly, for those who saw an increase in depression symptoms, the increase was temporary and did not have a strong impact on the participants' treatment outcome[57]. One study did show that in rare cases, such symptoms referenced can be severe (see "Potential Risks" above for more information)[54]. Ultimately, previous studies found that although some participants may experience transient increases in mental health symptoms, like depression and PTSD related symptoms, confronting past traumas is overall still a safe and effective intervention strategy. There is an option at the end of each session for 15-20 minutes for participants to de-stress and relax if they are emotionally distressed from session content.

The study therapist or study team member will be required to track each adverse event using the adverse events tracking spreadsheet and designated follow up questions. The adverse events tracking spreadsheet will include a description of the event, start and stop date, severity grade, relatedness grade, action taken, outcome, and whether the event qualifies as a serious adverse event. The follow up questions are as follows; "How has this impacted you? (to get at severity), Has this been affected by your participation in the treatment? (e.g., is group making your experience/symptoms worse, or is this directly caused by treatment). Follow up questions will be up to the study personnel dependent upon what the participation has shared. The study team will also record the event and its details using our electronic database, REDCap. The participant may be withdrawn per the discretion of the study therapist and clinical supervisors.

Guidelines for assessing the severity and study relatedness of each adverse events will follow the procedures outlined in Schnurr et al., 2022 and collaboratively determined by the study therapist and study team.

Severity:

Mild: Does not interfere with daily functioning/normal activities

Moderate: Interferes with normal activities to some extent

Severe: Interferes significantly with normal activities

Relatedness:

1. Not attributed to a study intervention
2. Possibly attributed to a study intervention
3. Attributed to a study intervention

An adverse event will be considered associated with the study if there is a reasonable possibility that the event was caused by the treatment or by an individual's participation in the research study. Any event with a reasonable causal relationship will be considered related.

The reporting period of adverse events begins from when participants sign the informed consent form until their final study visit (3-month follow-up visit), or until participants withdraw themselves from the study, whichever is sooner. All adverse events will be tracked using the Adverse Events tracking form. When adverse events occur, we will follow the Health Sciences IRB Unanticipated Problems Reporting Decision Tree.

Data and Safety Monitoring Plan/Data and Record Keeping:

We plan to utilize the UW ICTR Data Monitoring Committee (DMC) to oversee the study across all participating sites. The UW ICTR DMC is comprised of experienced members (core plus ad hoc) with expertise required to oversee this study. The DMC members will review protocol-specific reports created by statisticians using data pulled from the Research Electronic Data Capture (REDCap) data management tool. These standard reports will include an overview of study objectives, a review of actual and projected accrual rates, an evaluation of patient demographics for balance of randomization, and a summary of the number and seriousness of adverse events. An interim analysis of study results may be requested, and source documents may be reviewed to allow the DMC to independently judge whether the overall integrity and conduct of the protocol remain acceptable based on data provided and reported by the Principal Investigator. The DMC will make recommendations to the Principal Investigator that could include actions of continuation, modification, suspension, or termination.

In providing oversight for the conduct of this study, the ICTR DMC will meet every 6 months during the 3-year study to review all adverse events. Additional meetings may be scheduled as determined by the DMC or as requested by the PI. We will submit all reportable events to the DMC and the UW-Madison HS-IRB in accordance with their reporting guidelines. Additionally, [name] will review weekly progress reports that characterize the overall quality of each session and any unexpected events.

Data from this study will exist in a combination of electronic (computer) and paper files. We will use ICTR's instance of REDCap to support electronic data collection and storage. Data will be collected primarily on the REDCap Mobile App, a highly secure application that provides the ability to collect data offline. Offline data collection is required because of a lack of internet access at each prison. The REDCap Mobile App requires users to enter a username and unique pin to access the project, and data is encrypted on the device's hard drive. Data collected on the REDCap Mobile App will regularly be removed from the mobile device through transmission to the project's REDCap server. To protect the confidentiality of the electronic information, all electronic data will be coded, and the REDCap data collection project will not be stored with any personally identifying information. The code file with identifiers will always be stored separately from the coded electronic data under password protection.

Data collected on paper forms will be entered through REDCap's web-based application and stored on the project's REDCap server. The paper files will be coded, such that only a five-digit numerical code (not identifiable information such as the participant's name or birth date) will appear on the paper files. The paper files (i.e., questionnaires) will be stored in a locked file cabinet at the facility, only accessible by the DOC study therapists. At midpoint data collection, research staff will transfer the paper data from the first 6 sessions to a cabinet in a locked office in the P.I.'s laboratory in the Department of Psychiatry or locked filing cabinet in the Department of Psychology. At post-test data collection, research staff will transfer the paper data from the following 6 sessions to a cabinet in a locked office in the P.I.'s laboratory in the Department of Psychiatry or locked filing cabinet in the Department of Psychology. Access to the locked offices/cabinets will be limited to the members of the study team listed in this application.

The CAPS-5, treatment sessions, post-treatment focus groups (NIMH Branch), and post-treatment individual interviews (WPP Branch) will be recorded using DOC-approved digital audio recording devices. Audio recording devices will be password protected. Electronic data will be stored on a secure departmental server that is HIPAA compliant. To protect the confidentiality of the electronic information, all electronic data will also be coded, so the participant information will not be stored with any personally identifying information. The code file with identifiers will always be stored separately from the coded electronic data. The code file will be encrypted using a commercially available encryption program. The file will be unreadable without the encryption key. Therefore, even in the unlikely case that the files were somehow accessed inappropriately, the identifiable participant data would still be protected by the encryption. Hard copies of the encryption key for the code file will be stored by [name] (in a locked cabinet in his locked office) and by the Department of Psychiatry IT staff (in a locked cabinet in a separate locked office).

Study staff will use a HIPAA compliant UW-Madison Secure Zoom account to conduct virtual assessments. For these virtual visits, correctional staff will escort the participant to the private testing room but will not be present during the assessment.

Unspecified Future Research

The study data will be used only by [name] research team at UW-Madison. Only the UW-Madison study team personnel listed in this application will have access to the participant identifiers. The study data will be stored indefinitely in the database described in 2014-0350. Participants will have the option, at the time of consent, to give their permission to share data in the case of unspecified future research. Data will only be shared for future use with UW-Madison affiliates. We will not share data with any other companies or organizations, and any data that is shared will be stripped of identifiers.

Data that may be used for future research includes all symptom outcome measures collected throughout this study, and if a participant completed the CPT group. This data will be added to our current approved database protocol (2014-0350). The following information is included in this protocol, and applies to our future use of the data collected in this study:

#2014-0350: This project will involve no procedures or interventions. There will be no interaction with participants. This application is for the creation of a database only.

The database will be used to identify characteristics of incarcerated individuals (e.g., personality traits, mental health diagnoses, cognitive test scores, demographic data, etc.) that relate to criminal behavior. We will also use the database to retain the names of residents who have agreed to be contacted for future research studies. [name] will be the P.I. on any future studies that use data from this database, as well as on studies that contribute data to this database.

The data from this database exist in a combination of electronic (computer) and paper files. The electronic data are stored in single encrypted spreadsheet file, which will be stored on a secure password-protected Department of Psychiatry server. The paper files

will be stored in a locked cabinet in a locked office in the P.I.'s laboratory. To protect the confidentiality of the database information, all participant data will be coded, so the participant information will not be stored with any personally identifying information. The key that identifies individual participants will be encrypted and stored separately from the database file. All paper study data (e.g., questionnaires, surveys, etc.) will be stored in locked file cabinets in a locked office. Paper study data will include codes only (no names or other identifiable information in the paper records). All electronic study data will be encrypted and stored on a secure server. Because the majority of the data included in this database contains old data (although some data will be added from studies that are currently open), and because we will take sufficient care to protect the confidentiality of the study data, we believe that the risks to participants are minimal. The potential benefit to society is considerable; by developing a better understanding of the psychological, behavioral, demographic, and environmental characteristics that contribute to criminal recidivism, this research could lead to more effective diagnostic and treatment strategies for criminal offenders.

Any individual studies that contribute to this database which are currently open for data collection will remain open for data collection, and the data will be added to the database.

Since some of the individual studies that will contribute to the database have Certificates of Confidentiality (CoC), we will obtain an amended CoC for this research database.

The data in this database will be used only by [name] research team at UW-Madison to identify relationships between psychological assessment information, self-reported personality traits, and criminal history and behavior.

All future uses of the database will be submitted to the IRB. The study P.I. ([name]) will oversee all data transfer, storage, and analysis. Any unanticipated problems or complications will be reported immediately to the MR-IRB.

Human Participants Considerations Specific to Incarcerated Populations: Given the incarcerated status of potential participants, we outline several additional protections:

1. Potential research participants will be identified by the research team—no correctional staff will be involved in the identification of potential participants for this research study. Participants will be randomly selected from the database of residents that meet the eligibility criteria.
2. It will be emphasized to participants that participation in the study will have no effect on incarceration status, and that study results will not be shared with correctional staff. In addition, it will be emphasized to correctional staff that individual study results will not be shared with residents or correctional staff.
3. The consent, assessment and treatment will occur in a private room, without the presence of correctional officers.

4. The questionnaires and treatment protocol used in this study are common techniques for healthy populations, and do not provide any risk to residents that would not be encountered by non-incarcerated populations. We thus anticipate the creation of only minimal risk from these procedures, similar to those that would be encountered in non-incarcerated populations.
5. In this study we are enrolling incarcerated individuals who may or may not have completed high school education and may have limited reading skills. We are taking several precautions to ensure that participants in this study can understand the written consent information. To ensure that all study information is presented in language that is understandable to the resident, all consent material is written so as to be readable to an individual with a 4th grade reading level. During the consent procedure, residents are encouraged to ask the research staff for definitions of any words that they do not understand. We will exclude any participants who have an IQ below 70 or reading level below 4th grade. Thus, we can be sure that all participating residents will have sufficient reading skills to make informed decisions throughout the study procedures.

Under DHHS 45 CFR 46.306(a)(2), biomedical or behavioral prisoner research may only be conducted if the research involves specific criteria. This proposed study satisfies criterion (i) “Study of the possible causes, effects, and processes of incarceration, and of criminal behavior”.

Regarding criterion (i), this study is designed to identify psychological and affective factors that may predispose a person to criminal behavior and incarceration in order to effectively design and implement treatment programs. Specifically, PTSD severity has been linked to increased risk of recidivism, and trauma is a hypothesized precursor to criminality [2,3,10].

Statistical Considerations:

NIMH Branch:

The primary goal of this study is to establish feasibility of the target intervention (CPT). Hence, we base our power analysis on the “retention” data collected Specific Aim #1 (i.e., the percentage of participants completing the CPT intervention). A sample size of $n = 32$ for the CPT group will provide 80% power to perform a one-sided test where the null hypothesis is 60% retention (approximately the lowest retention rate reported in previous CPT trials, versus the alternative hypothesis of 80% retention (our study goal), with a Type I error of 5%.

WPP Branch:

The primary goal of this study is to examine efficacy of the target intervention (CPT). Therefore, we will use the same target sample size ($n = 32$) used to establish feasibility of the target intervention, as this reflects the number of participants needed to conduct powered analyses based on the lowest retention rate reported in previous CPT trials.

Both the NIMH and WPP branches satisfy this condition with sample sizes of $n = 60$ for the CPT groups and sample sizes of $n = 60$ for control groups (WPP branch only).

REFERENCES

1. James, D. J., Glaze, L. E., & Statisticians, B. (2006). *Bureau of Justice Statistics Special Report Highlights Mental Health Problems of Prison and Jail Inmates*.
4. Kessler, R. C., Wai, T. C., Demler, O., & Walters, E. E. (2005). Prevalence, severity, and comorbidity of 12-month DSM-IV disorders in the National Comorbidity Survey Replication. In *Archives of General Psychiatry* (Vol. 62, Issue 6, pp. 617–627). <https://doi.org/10.1001/archpsyc.62.6.617>

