Participants will be randomly assigned to the CPT or the active control groups (randomization process specified in “Randomization and Blinding”). The CPT group will engage in 12, 90-minute treatment sessions (18 hours total). With the optional opportunity to take 15-20 minutes after each session to de-stress and calm down if necessary. These sessions will take place over 6 to 12 weeks, depending on session frequency. CPT group-members are also asked to complete weekly homework (approximately 12 hours total). A maximum of 8 participants, but no less than 3 will be included in each CPT group. When the waitlist control group reaches the treatment phase, if the participant count fall below 3, additional participants will be enrolled to maintain sufficient numbers. Data collection during treatment will mirror that of the active waitlist control group. Participants will be notified via institutional mail which group they have been enrolled in.

In addition to the treatment groups, CPT and control group members will complete a PCL-5 at the beginning of each session. As well as, pre-treatment testing session two weeks prior to the start of treatment. After treatment session 5, CPT and control group members will complete mid-treatment testing assessments. Participants will be called down individually to complete these assessments in a private room with a research assistant after completing the 5th therapy session, but before completing the 8th therapy session. CPT and control group members will then complete post-treatment testing within one week after completing week 6 of treatment. One month after the treatment is completed, CPT and control group members will complete follow-up testing and interviewing about their experience in the treatment groups and will have one follow up CPT session 6-8 weeks post-treatment. Post-treatment and one-month follow up- testing will follow the same procedure as pre-treatment and mid-treatment testing. Final follow-up will occur three months after the end of treatment. Procedures will be the same as other timepoint follow-ups. CPT and control group members will be asked to complete 18 sessions in total (pre-treatment, mid-treatment, post- treatment, one-month follow up-testing, three-month follow-up treatment, 12 group sessions and one follow-up CPT session).

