[†] For the NIMH branch, any historical data (i.e., information that is stable and is not expected to change over time) that has already been collected through protocol 2014-1106, we will obtain this data from the PI's database (2014-0350) and will not re-administer these assessments under the current protocol.

Measures and Assessments:

NIMH Branch: If participants have completed any of the following measures or assessments as part of study 2014-1106 two months or less from the time of enrollment for this study, we will not complete them again. Instead, we will obtain this data from the PI's database (2014-0350).

WPP Branch: We will not use previously-collected data from any participants who may have completed these assessments through study 2014-1106, given the confidentiality rules outlined in that study. Participants who consent to the WPP branch will be re-administered each assessment.

Baseline Assessments:

These measures will be collected prior to the study and group assignment (across multiple visits) and used to examine potential moderating variables (see “Measurement of Specific Aims”).

PTSD: We will determine PTSD diagnosis through the PCL-5. The PCL-5 is a 20-item self-report measure that assesses for DSM-5 symptoms of PTSD [52].

NIMH Branch: If PTSD status has been assessed through protocol 2014-1106 more than two months prior to baseline assessments, we will update this information during baseline assessments as needed. To update symptoms, study staff will meet with the participant to re-evaluate current symptoms of PTSD

Trauma History: We will administer the Trauma History Questionnaire (THQ)[†] in conjunction with the CAPS-5. The Trauma History Questionnaire (THQ) is 24-item scale assessing experiences of traumatic events [21]. We will also administer two self-report questionnaires that assess distinct (but overlapping) aspects of lifetime trauma and stress exposure: The Life Events Checklist-5[†] (LEC-5; a 17-item self-report measure of potentially traumatic (i.e., life-threatening or severely harmful) events during the participant's lifetime. [22] The LEC-5 will be administered the first time the PCL-5 is completed. The Childhood Trauma Questionnaire[†] (CTQ; 29-item scale assessing severity of physical abuse, physical neglect, emotional abuse, emotional neglect, and sexual abuse under age 18) [23].

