To ensure that our randomization process results in treatment groups that are balanced on key variables that might affect treatment response, participants will be assigned to groups through stratified randomization, in which randomization occurs within specific strata of different potential moderating variables and assures equal assignment to each group across these variables. Participants will be stratified/randomized based on PTSD severity (PCL-5 total score).. The stratified randomization will use group code numbers (1 & 2) rather than the intervention title, thus eliminating any chance of systematically biasing the group assignment.

While it is impossible for the therapists and participants to be blind to the group assignment, the research members performing the pre-treatment, mid-treatment, post-treatment, one-month and three-month follow-up assessments will be blind to the group assignment. The study therapist will not conduct assessments once participants have assigned to their respective treatments (e.g., pre-, mid-, post-, or follow-up assessments). Additionally, one graduate research assistant will schedule

participants according to the randomization, thus minimizing the possibility of systematically biasing the outcome and mediator assessments.

Treatment:

NIMH & WPP Branches:

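### The WPP plan conflicts on whether the pre-treatment battery precedes group assignment, and does not say which PCL-5 is the analysis baseline

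*Combined protocol and SAP*

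**What the plan says.** Passages that suggest assignment comes first:

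- Research Design and Procedures (WPP Branch) opens with random assignment and ends that paragraph with "Participants will be notified via institutional mail which group they have been enrolled in". The next paragraph describes testing for members of the CPT and control groups and includes the pre-treatment test: "As well as, pre-treatment testing session two weeks prior to the start of treatment".
- Randomization and Blinding (WPP Branch) says: "The study therapist will not conduct assessments once participants have assigned to their respective treatments (e.g., pre-, mid-, post-, or follow-up assessments". It also says that "the research members performing the pre-treatment, mid-treatment, post-treatment, one-month and three-month follow-up assessments will be blind to the group assignment".

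Passages that suggest measurement comes first:

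- Baseline Assessments says: "These measures will be collected prior to the study and group assignment (across multiple visits) and used to examine potential moderating variables". Its first entry is PTSD: "We will determine PTSD diagnosis through the PCL-5".
- Randomization and Blinding stratifies on the PCL-5 total score.
- Monitoring and Reporting Adverse Events calls the first of the five BDI-II timepoints baseline.

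On blinding, the plan accepts that "it is impossible for the therapists and participants to be blind to the group assignment".

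On use of the scores, the Questionnaires section lists a battery repeated at the pre-, mid-, post-, one-month and three-month timepoints. It includes the PCL-5, BDI-II, BAI, Beck Hopelessness Scale and Posttraumatic Cognitions Inventory. Under Measurement of Specific Aims (WPP Branch), the groups are compared on change from pre- to post-intervention, with IQ and age as covariates. The moderator and mediation regressions adjust for pre-intervention scores.

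**The concern.** The comparison of arms on the primary outcome is a difference in change scores, so it depends on the pre score as much as on the post score. If participants have already been told whether they start CPT now or wait, that knowledge could affect how they rate their symptoms at the pre-treatment session. Blinding the assessor gives no protection, because the participant supplies the answers. The direction of any shift cannot be predicted: people told to wait might report more distress or less, and so might people told that treatment is about to begin.

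The same scores feed the secondary outcomes (BDI-II, BAI) and the mediators (hopelessness, cognitions). A baseline affected by arm would therefore reach beyond the primary analysis.

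**Working it through.** **1. Does the text fix the order?**

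| Section | What it implies | Strength |
|---|---|---|
| Randomization and Blinding, therapist sentence | Pre-treatment test after assignment | Direct, but inside a list of examples |
| Randomization and Blinding, assessor blinding | An allocation may already exist at the pre-treatment test | Indirect; trivially true if it does not |
| Research Design and Procedures (WPP) | Test taken by people who already have an arm label | Indirect; text order is not a timetable |
| Baseline Assessments | Listed measures, including the PCL-5, before assignment | Direct, for the listed measures |
| Stratification factor | Some PCL-5 score before randomisation | Necessary, but does not say which score |
| Adverse-event monitoring | Baseline and pre-treatment may be one timepoint | A label, not an ordering rule |

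The two direct statements point in opposite directions, and no other passage resolves them.

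**2. Which PCL-5 is the baseline?** Eligibility needs a PCL-5 score of 31 or more within two months of starting treatment. That score could serve for stratification, so stratification does not force the battery to come first. The plan never says whether the eligibility score and the battery score are the same administration, or which one the effectiveness analysis uses.

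**3. What about the other scales?** The Baseline Assessments list does not contain the BDI-II, BAI, Beck Hopelessness Scale or Posttraumatic Cognitions Inventory. For these the plan states no measurement before assignment, apart from the baseline label given to the first BDI-II.

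**4. How would a shift enter the analysis?** Let *b* be the between-arm difference in the pre score caused by knowing the arm.

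- Change score: the estimated difference in change moves by *b*, one for one.
- Regression of the post score on arm and pre score, with slope β on the pre score: the estimated arm effect moves by β × *b* in size. For β between 0 and 1 this is part of the shift.

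**5. How large could the effect be?** No figure in the plan depends on this timing. Its only sample-size calculation (n = 32) concerns retention, and it gives no SD for PCL-5 change. What follows is therefore illustration.

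Inputs:

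- 40 per arm, from the WPP total of 80. The sex split printed beside it, 40 + 60, sums to 100, or 50 per arm. Statistical Considerations gives 60 per group, so 60 is the upper case.
- SD of change 15, range 12 to 18 (assumed).
- Shifts of 2, 3 and 5 points (assumed).
- No true effect, two-sided 5% test, normal approximation, no allowance for clustering by therapy group.

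Formulas:

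- SE = SD × √(2/n) = 15 × √(2/40) = 3.35
- Rejection probability = P(Z > 1.96 − b/SE) + P(Z < −1.96 − b/SE)

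For b = 3, b/SE = 0.894, and the sum is 0.145.

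| Per arm | SD | SE | b = 2 | b = 3 | b = 5 |
|---|---|---|---|---|---|
| 40 | 12 | 2.68 | 0.116 | 0.201 | 0.462 |
| 40 | 15 | 3.35 | 0.092 | 0.145 | 0.320 |
| 40 | 18 | 4.02 | 0.079 | 0.116 | 0.237 |
| 60 | 12 | 2.19 | 0.150 | 0.278 | 0.626 |
| 60 | 15 | 2.74 | 0.113 | 0.195 | 0.447 |
| 60 | 18 | 3.29 | 0.093 | 0.150 | 0.331 |

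**The case against.** A reader might infer that the protocol definitely takes the analysed baseline after participants have learned their arm. The documents do not support that.

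- Baseline Assessments is explicit that its measures come before assignment, and the PCL-5 heads its list.
- Several sections use baseline where others use pre-treatment, so the two may be one visit.
- The order of sentences in Research Design and Procedures is not chronological. The waitlist group's later treatment phase is mentioned before the notification letter, so the position of that sentence does not date the letter.
- The list that contains the pre-treatment test is a loose parenthesis in a sentence about who does not assess.
- An allocation that exists is not the same as one the participant knows.

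A reader might also infer that any such bias would be irreparable. For the PCL-5 that is wrong: stratification requires a score before randomisation, and that score could replace the later one. The error rates are also conditional on an assumed SD and assumed shifts. They are not estimates of this trial's risk.

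All of this stands against the stronger readings. It does not remove the conflict between sections, the missing mailing date or the unnamed baseline. It also supplies no fallback for the secondary outcomes and mediators, for which no earlier score is specified.

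**Conclusion.** The concern holds as an unresolved conflict that permits an unblinded, self-reported baseline. It does not hold as proof that the plan prescribes one. If the battery is completed before notification, there is no bias from this source. If it is completed afterwards, an arm-related shift enters the change-score contrast in full and the covariate-adjusted models in part.

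With 40 per arm, an assumed SD of change of 15 and no true effect, shifts of 2, 3 and 5 points give type I error of about 9%, 15% and 32%. For a 3-point shift the range is 12% to 28% over SD 12 to 18 and 40 to 60 per arm. The documents offer no evidence on whether a shift would occur, how large it would be or in which direction.

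The PCL-5 analysis could be rescued with the earlier score. The plan specifies no equivalent for the BDI-II, BAI, hopelessness and cognitions scales, so the order of steps matters most for them.

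**What to change.** - In Research Design and Procedures (WPP Branch), Baseline Assessments, and Randomization and Blinding, state one order: in each round the full pre-treatment battery is completed before randomisation, and assignment letters are mailed only after the round's last battery.
- In Randomization and Blinding, delete the pre-treatment test from the list of post-assignment assessments.
- In the WPP analysis of effectiveness, name as baseline a PCL-5 completed before randomisation and notification. Once the battery comes first, its own PCL-5 qualifies.
- If any round has already taken the battery after notification, use the eligibility or stratification PCL-5 as the baseline for the primary outcome in that round. That score may be up to two months older than the start of treatment.

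The cost is protocol wording and the order of existing steps, with no added visit. The downside is that randomisation, scheduling and mailing must fit into the roughly two weeks before session 1. The documents give no turnaround times, so the study team should confirm that this is workable at each facility.
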